Aim 1: Discover Phase (3 months). Using iterative and participatory methods, we will interview up to 15 clinicians from FHQCs affiliated with the WWAMI region Practice Research Network (WPRN, a collaborative group of primary care practices through the states of Washington, Wyoming, Alaska, Montana and Idaho to facilitate innovative community-based research), and observe them in routine practice to identify usability challenges. Contribution to the Center: Data from this phase will be used to inform the Typology of EBPI Targets.

Aim 2: Design/Build Phase (6 months) After identification of potential targets, the research team will work via Zoom teleconferencing with the original clinicians from the discover phase and 0-5 new clinicians to engage in a rapid cycle of iterative prototype development and testing (e.g., storyboarding, paper prototypes) of BA modifications. The build of these modifications will include the development of intervention prototypes for user testing and refinement with input from these care managers. Contribution to the Center: Data from this phase will be used to inform the Matrix of EBPI Modifications.

Aim 3: Test Phase (15 months). We will test and compare the BA modification (modBA) to usual care in a small non-randomized trial. We will assign all provider teams (therapist & care manager(s)) in the clinic to use modBA with 10 patients per team for a total of 40 patients. We will then compare patient outcomes for those receiving modBA vs. 40 patients receiving usual clinic care. **H1:** Modifications developed in the Design/Build phase for targets identified in the Discover Phase will result in better usability (System Usability and User Burden Scales) compared to usual care.

H2: modBA will be more effective than usual care on improving clinical outcomes of functional disability (Sheehan Disability Scale [SDS]), change in depression symptoms over time (PHQ-9 total score), and change in anxiety symptoms over time (GAD-7 total score).

1.6 Study design. Provide a one-sentence description of the general study design and/or type of methodology.

Your answer will help HSD in assigning applications to reviewers and in managing workload. Examples: a longitudinal observational study; a double-blind, placebo-controlled randomized study; ethnographic interviews; web scraping from a convenience sample of blogs; medical record review; coordinating center for a multi-site study.

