We will iteratively improve designs through usability testing with the clinicians and care managers. For example, if the *Discover* phase finds that the BA process needs to include no more than 3 steps, we may take the following steps:

1. The design team will create (for example) 3 different ways a BA component (such as activity charting) could be condensed, modified, or distributed differently in a workflow. These different processes will be depicted in electronic story boards.
2. The story boards will be shown to the clinicians with accompanying intervention materials (manuals, etc.). During the presentation, clinicians will be asked for their assessment of perceived usability (ease of learning, potential for use in clinic, perceived burden, and acceptability) for each iteration. These assessments will be both quantitative (System Usability Scale) and qualitative (Think Aloud). Quantitative data will be stored in the REDCap database, as will audio recordings of the Think Aloud Assessment.
3. Designers will then create a new version of the modification using information from all three storyboard assessments. The next version will be assessed using the processes described in step 2. This will continue until we reach a SUS scale score of .80. A final prototype will undergo initial feasibility evaluation in pilot field deployments with each clinician using the prototype with one depressed patient, with a PHQ-9 score between 10-20 (recruited from their WPRN clinic). Once we have completed the redesign of the EBPI so that it (1) meets needs of its clinicians and patients (i.e., is useful), and (2) is easy to use and understand (i.e., is usable), we will move to the *Test* phase (Phase 3) of this study.

Phase 3 Testing

We will conduct a pilot study comparing the modified EBPI to usual care at Bighorn Valley Health Center (BVHC). The EBPI itself (Behavioral Activation) will not change for the patients, but rather we will modify how Therapists and Care Managers at BVHC are sharing the tasks involved in Behavioral Activation. The modifications will also help guide Therapists and Care Managers as they decide how and

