when to use BA in specific clinical situations. The Therapists and Care Managers of some clinics in the BVHC network have already implemented this modified approach, and the goal is to have all clinics in the network learn and use the model. The Therapists and Care Managers will receive additional training and guidance from the study team to achieve this modification, but the patients' clinical care visits will not change. During the additional training, UW and Stanford study staff members will provide consultation on BVHC patient cases in order to provide support for any cases where BVHC clinicians are having difficulty using BA. During these discussions, no staff from the UW or Stanford team will ever know any identifiable information about the patients. However, both UW and Stanford staff members will have access to clinician participants' identifiable information from training/support activities with the clinicians. We will use pre-existing clinic measures to collect patient outcome data for patients whose providers are using the modified BA model. We will also collect patient outcomes using the same pre-existing clinic measures for patients whose providers are providing usual care. We will then compare outcome data for each type of care. A total of 11 clinicians and 80 patients will be recruited for Phase 3.

Clinician Procedures:

Clinician training in BA. UW team staff will train clinicians in modified Behavioral Activation elements per the protocol used by the AIMS Center, which includes training in basic brief treatment skills, therapeutic elements of the intervention and therapy process. The training will also include modifications developed via clinician/research staff co-design in Phase 2.

Note: These modifications will be developed in Phase 2, and new materials will be submitted to the IRB prior to beginning Phase 3.

Training will be followed by simulated case training. Once clinicians finish the training and begin using the modified BA with patients, we will use a self-report checklist and open-ended questions regarding the use of modified BA to measure clinicians' adherence to the model.

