Participants must be 18 years old or older, suffering from mild to moderate depression. The site champion will identify potential participants from their electronic health records (EHRs) who score between 10 and 20 on the PHQ-9. Patient procedures include:

- Up to 40 patients who are already receiving care at BVHC will receive care via the BA task-sharing model
- We will also include a sample of up to 40 other patients who are already receiving care at BVHC (but not yet receiving care via the modified BA model) who will continue to receive their usual care
- Patients will complete weekly PHQ and GAD (already being collected by BVHC as part of usual care). This includes both the patients who are receiving care via the BA task-sharing model and those who are receiving care without the model
- We will collect historic patient data (PHQ and GAD, already collected by BVHC and agreed to by patients) for all patient participants. This includes both the patients who are receiving care via the BA task-sharing model and those who are receiving care without the model.
- We will collect 3-month follow up patient data (PHQ and GAD, already collected by BVHC and agreed to by patients) for all patient participants. This includes both the patients who are receiving care via the BA task-sharing model and those who are receiving care without the model.
- We will ask up to 10 patients who received care via the BA task-sharing model to complete exit interviews to give their perspective on the care they received. Patients will be consented for these

interviews, as we will then be asking patients to complete research activities that are beyond activities already completed during their usual care. Patients will be paid \$25 for the exit interviews.

- 5.2 Data variables.** Describe the specific data you will obtain (including a description of the most sensitive items). If you would prefer, you may upload a list of the data variables to the **Supporting Documents** SmartForm instead of describing the variables below.

Clinician Data:

Phase 1 & 2 qualitative clinician interviews:

We request flexibility in qualitative interviewing questions with clinicians during Phase 1 and 2 which will include:

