Aim 1: Discover Phase (3 months). Using iterative and participatory methods, we will interview 10 clinicians from FQHCs affiliated with the WWAMI region Practice Research Network (WPRN, a collaborative group of primary care practices through the states of Washington, Wyoming, Alaska, Montana and Idaho to facilitate innovative community-based research), and observe them using PST-PC to identify usability challenges.

[figure not shown]
Contribution to the Center: Data from this phase will be used to inform the Typology of EBPI Targets.

Aim 2: Design/Build Phase (6 months) After identification of potential targets, the research team will work with the original 10 clinicians to engage in a rapid cycle of iterative prototype development and testing (e.g., storyboarding, paper prototypes) of BA modifications. The build of these modifications will include the development of intervention prototypes for user testing and refinement with input from these care managers.

Contribution to the Center: Data from this phase will be used to inform the Matrix of EBPI Modifications.

Aim 3: Test Phase (15 months). We will test and compare the BA modification (Task Sharing) to usual care in a small non-randomized trial. We will assign all provider teams (therapist & care manager(s)) in the clinic to use Task Sharing with their patients. We will then compare patient outcomes for those receiving Task Sharing vs. patients receiving usual clinic care. H1: Modifications developed in the Design/Build phase for targets identified in the Discover Phase will result in better usability (System Usability and User Burden Scales) compared to usual care. H2: Task Sharing will be more effective than usual care on improving clinical outcomes of functional disability (Sheehan Disability Scale [SDS]), change in depression symptoms over time (PHQ-9 total score), and change in anxiety symptoms over time (GAD-7 total score).

This study directly addresses IOM report recommendation 3-1: conduct research on psychosocial intervention elements and NIMH SP 4.1 Improve efficiency and effectiveness of existing mental health services.

SIGNIFICANCE

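### Usual-care controls are defined by provider in one place and by the patient's own treatment in another, which lets untreated patients of modBA-trained teams serve as controls

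*Combined protocol and SAP*

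**What the plan says.** **Provider-level wording.** In section 5.1, Phase 3 Testing, the modBA group is "patients whose providers are using the modified BA model". For the comparison group the text says: "We will also collect patient outcomes using the same pre-existing clinic measures for patients whose providers are providing usual care".

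**Patient-level wording.** The patient procedures in the same section give up to 40 patients who receive care through the model, and up to 40 "other patients who are already receiving care at BVHC (but not yet receiving care via the modified BA model", who stay on usual care. The control patient's provider is not mentioned.

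**Allocation.** Section 1.5, Aim 3, calls the study a "small non-randomized trial" and assigns all provider teams "in the clinic to use modBA with 10 patients per team for a total of 40 patients". The Specific Aims of the grant narrative likewise assign all teams "in the clinic to use Task Sharing with their patients", without a per-team number. Neither names a usual-care team.

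**Roll-out and discretion.** Section 5.1 says some clinics in the Bighorn Valley Health Center (BVHC) network already use the model and that all are meant to adopt it. It also says: "The modifications will also help guide Therapists and Care Managers as they decide how and", and the sentence goes on to the timing of BA in particular clinical situations.

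**Analysis.** The Data analysis section of the narrative plans descriptive summaries by clinician and by treatment, Cohen's d and a t-test for patient outcomes. It states no adjustment for baseline or for confounders.

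**The concern.** In a non-randomized comparison, the rule that sorts patients into arms determines what the contrast estimates. Here the two wordings can sort the same patient differently. Take a patient with a PHQ-9 of 14 on the caseload of a trained team that has not used modBA with that patient. Under the patient-level wording this is an eligible control. Under the provider-level wording it is not, because the provider is no longer giving usual care.

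Two distortions could follow if such patients become controls. If teams use modBA where they think it fits, treated and untreated patients may differ in prognosis. And the untreated patients are still seen by staff trained in the model, which would dilute any real effect. H2 states that modBA will be more effective than usual care, and the pilot is meant to inform a larger trial. A distorted PHQ-9 or GAD-7 effect size would be carried forward into that planning.

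**Working it through.** **1. The plan's own figures.** 40 modBA + 40 usual care = 80 patients, which matches the stated total. 40 / 10 per team = 4 teams. (The clinician procedures in 5.1 give the target of 10 per clinic rather than per team.) No power calculation is stated, so none can be reproduced.

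**2. The two wordings side by side.**

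| Patient | Provider-level wording | Patient-level wording |
|---|---|---|
| Provider not yet using modBA | control | control |
| Trained team, treated with modBA | modBA | modBA |
| Trained team, not treated with modBA | not a control | eligible as control |

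Only the third row differs.

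**3. Can the third row be avoided?** Once all teams in the clinic are trained, that clinic has no provider giving usual care. A concurrent control from it can only come from the third row. The alternatives are other clinics not yet converted, or dates before training. No section says which clinics, teams or dates supply the controls.

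**4. How modBA patients are chosen.** The plan gives a number per team but no rule such as consecutive or random selection. The site champion's search of the health record by PHQ-9 score identifies potential participants; it does not settle the arm.

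**5. Whether the data would allow repair.** Section 5.2 and the list in 5.7 name demographics, process measures, PHQ-9 and GAD-7. They do not name provider, clinic or training date, and BVHC de-identifies the data before sending them. The planned summaries by clinician need a field that these lists do not secure.

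**6. Illustration of size.** The inputs below are assumptions, not figures from the plan: no true effect, SD = 1, independent patients, two-sided alpha 0.05, 40 per arm. Let a share f of controls be untreated patients of trained teams whose outcome is worse by g SD.

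- Bias b = f × g.
- SE = √(2/40) = 0.224 SD.
- Rejection probability = Φ(b/SE − 1.96) + Φ(−b/SE − 1.96).

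| f | g | b (SD) | Rejection probability |
|---|---|---|---|
| 0 | any | 0 | 5.0% |
| 0.25 | 0.2 | 0.05 | 5.6% |
| 0.5 | 0.3 | 0.15 | 10.3% |
| 0.5 | 0.5 | 0.25 | 20.1% |
| 1 | 0.5 | 0.50 | 60.9% |

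For scale, the effect detectable with 80% power is (1.960 + 0.842) × 0.224 = 0.63 SD.

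**7. An extreme case.** Suppose each team treats the more suitable half of its caseload, sorting is perfect, every control comes from the other half, and suitability correlates rho with outcome. The mean of the upper half of a standard normal is 0.798, so the spurious d is 2 × 0.798 × rho = 0.16, 0.32 and 0.48 at rho = 0.1, 0.2 and 0.3. If controls come only from untrained providers but the modBA arm is still hand-picked, half of this remains: 0.08, 0.16 and 0.24. Fixing the control rule alone is therefore not enough; the modBA arm needs a selection rule too.

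**The case against.** A reader might infer that the two wordings contradict each other. They do not. Patients of providers who have not yet adopted modBA satisfy both, and the phrase about not yet receiving the model fits the staged roll-out in 5.1. The consent table in 8.2 also ties patients' exposure to when their therapists begin coaching, which is a provider-level trigger.

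A reader might also infer that confounding by indication is built into the design. The documents do not establish that. No section says teams pass over unsuitable patients. The guidance text concerns when to use BA, not when to use the task-sharing model, so a team that holds back BA may still be following the model. A patient who arrives after a team's 10 places are filled is untreated because of order of arrival, not because of a judgement about suitability.

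The direction is not settled either: selection could favour modBA while contamination shrinks the contrast. And the Data analysis section says the pilot's analyses are mainly descriptive.

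All of this stands, and it limits the claim. It does not close the gap. Nothing excludes the third-row patient, the all-teams assignment leaves no other concurrent source within the clinic, and H2 and the t-test still compare the groups. Selection by suitability is also plausible on the plan's own evidence: 5.1 and 5.2 list lack of motivation, profound pessimism and trauma exposure among the problems clinicians find hard to address with such interventions.

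**Conclusion.** The concern holds as an under-specified control rule. The patient-level wording permits untreated patients of trained teams as controls, and the all-teams assignment makes them the only concurrent source within the clinic. The comparison is then open to selection by perceived suitability and to contamination, with no planned adjustment.

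How much this matters cannot be determined from the documents. The illustrations run from 0, if no such patient is used, to about 0.5 SD in the extreme cases. They rest on assumed values of f, g and rho and, at the upper end, on every control being an untreated patient of a trained team. They show that the possible distortion can approach the 0.63 SD that 40 per arm could detect; they do not estimate what will occur.

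The firmer inconsistency is between the provider-level description in 5.1, which needs providers giving usual care, and the Aim 3 statements, which leave none in the clinic after training.

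**What to change.** Apply the provider-level rule to both arms and amend the patient procedures in 5.1 accordingly, before any control data are pulled:

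- **modBA arm:** consecutive eligible patients (PHQ-9 10-20) whose index visit is with a team that has completed modBA training, whether or not modBA elements were then used. Report checklist use as adherence, not as a condition of entry.
- **Usual-care arm:** eligible patients whose index visit is with a provider not yet trained in modBA. Patients of trained teams are excluded.
- **Source of controls:** state which clinics and dates supply them, and reconcile 5.1 with both versions of Aim 3. The Phase 3 text of the grant narrative, which has therapists randomized with 5 patients each, needs reconciling at the same time.
- **Data:** add coded provider, clinic and training date to the de-identified extract.
- **Analysis:** prespecify adjustment for baseline PHQ-9 and GAD-7, which are already collected.

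The cost is protocol wording and a few fields in the extract. There are two downsides. Some modBA-arm patients will have received little of the model, so the estimated effect may be smaller. And controls must then come from other clinics or earlier dates, so clinic or calendar-time confounding will remain; baseline adjustment will not remove all of it, and it should be reported as a limitation.

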Phase 1 & 2: We will recruit clinicians via informational letters about the study and talking points for phone scripts.

Phase 3: Clinician participants will be recruited based on past participation in the Design phase of this study. Some new clinician participants will also be recruited for Phase 3 based on recommendation of these past participants who completed the Design phase and work in the same clinic. Participants will be recruited by email.

Patient Participants: Patients will be identified through electronic health records with a PHQ-9 score between 10-20. Patients will only be contacted and recruited if they are chosen to complete exit interviews. For those identified for exit interviews, they will be approached by BVHC staff either in person or via email, the study will be briefly explained to them, and then they will be asked if they are willing to complete an exit interview. For those willing, their contact info will be provided to UW study staff to reach out for further explanation and consent.

Note that site champions will complete CITI Human Subjects Protection training and will be trained by study staff regarding appropriate procedures for recruitment. We will make it clear to site champions that the consequences of coercing patients into study participation will be removal from the study protocol.

- b. Upload descriptions of each type of material (or the materials themselves) to the **Consent Forms and Recruitment Materials** SmartForm of **Zipline**. If you will send letters to the subjects, the letter should include a statement about how you obtained the subject's name, contact information, and any other subject-specific information (such as a health condition) that is mentioned in the letter.

HSD encourages researchers to consider uploading descriptions of most recruitment and screening materials instead of the materials themselves. The goal is to provide the researchers with the flexibility to change some information on the materials without submitting a Modification for IRB approval of the changes. Examples:

- *You could provide a list of talking points that will be used for phone or in-person conversations instead of a script.*

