- Qualitative treatment experience questions

5.3 Data sources. For all types of data that you will access or collect for this research: Identify whether you are obtaining the data from the subjects (or subjects’ specimens) or whether you are obtaining the data from some other source (and identify the source).

If you have already provided this information in Question 5.1, you do not need to repeat the information here.

We will obtain clinician data from the subjects. We will obtain all patient data from their EHR except for patients who agree to complete exit interviews. For those patients, data will also be collected directly from the subject.

5.4 Retrospective/prospective. For all types of data and specimens that you will access or collect for this research: do all data and specimens to be used in the research exist (for example, in subjects’ medical records) at the time this application is being submitted for initial review?

	No
	Yes

Include any necessary comments or explanation below (Note that for most studies this can be left blank):

5.5 Identifiability of data and specimens. Answer these questions carefully and completely. This will allow HSD to accurately determine the type of review that is required and to assist you in identifying relevant compliance requirements. Review the following definitions before answering the questions:

Access means to view or perceive data, but not to possess or record it. See, in contrast, the definition of “obtain”.

Identifiable means that the identity of an individual is or may be readily (1) ascertained by the researcher or any other member of the study team from specific data variables or from a combination of data variables, or (2) associated with the information.

Direct identifiers are direct links between a subject and data/specimens. Examples include (but are not limited to): name, date of birth, medical record number, email or IP address, pathology or surgery accession number, student number, or a collection of your data that is (when taken together) identifiable.

Indirect identifiers are information that links between direct identifiers and data/specimens. Examples: a subject code or pseudonym.

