between modified BA and usual care will be plotted using a dotplot and tested using a *t*-test using the SUS and UBS as dependent variables. **H2: Fidelity/Competence:** A similar strategy (dotplot, *t*-test) will be used with number of hours to reach certification. Number of sessions with fidelity scores <4 (“good”) will be summarized as proportions, both by clinician and by treatment. Between-treatment differences will be tested with a 2-sample proportion test. (Future analyses with larger sample size will use a generalized linear mixed model approach to account for the nested data^{89,90}.) **H3: Patient Reported Outcomes.** Histograms and kernel density estimates will be plotted by treatment condition to explore differences on depression outcomes (PHQ-9 total score) and overall daily functioning (SDS). Descriptive statistics (*M* and *SD*) will also be examined by clinician and by treatment, using Cohen’s *d* as an effect size summary. A *t*-test will be used to examine treatment differences in patient outcomes. Of ultimate interest is whether the modified treatment has its impact on patient outcomes through enhanced usability and clinician fidelity. We will use graphical summaries of the data to explore the relationships that are consistent with mediation (e.g., correlation of usability with patient outcomes [b pathway], and treatment differences on patient outcomes with fidelity partialled out [c’ pathway]). The primary focus here is whether the data and relationships appear consistent with mediation, as opposed to a formal test, which will be dramatically under-powered.

Power and Sample Size. Sample sizes for Aims 1 and 2 were based on estimates from the UCD literature on necessary number of participants to capture critical design information, where the recommendation is 5-10 end users. As Aim 3 is focused on gathering information (feasibility, recruitment and retention rates, response and attrition rates, etc.) for a future R01 application, the sample size was set primarily for practical reasons and used estimated effect sizes, rather than being driven by hypothesis testing.

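### The 3-month PHQ-9 and GAD-7 exist only if the clinic happens to record them, so a comparison of the available scores may be biased in a direction that cannot be known in advance

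*Combined protocol and SAP*

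**What the plan says.** Section 5.1 (Phase 3, Patient Procedures) describes two groups of patients already in care: "Up to 40 patients who are already receiving care at BVHC will receive care via the BA task-sharing model", and "a sample of up to 40 other patients who are already receiving care at BVHC" who continue usual care. On outcome scores it says "Patients will complete weekly PHQ and GAD (already being collected by BVHC as part of usual care" and, for follow-up, "We will collect 3-month follow up patient data (PHQ and GAD, already collected by BVHC", which it intends for every patient in both groups. No start point or window is given for the patients' 3 months.

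Section 5.3 names the source: "We will obtain all patient data from their EHR except for patients who agree to complete exit interviews". The exit interviews are qualitative and cover up to 10 modBA patients. Section 4.2 adds: "Patients will only be contacted and recruited if they are chosen to complete exit interviews". Section 5.2 also lists process measures from the record, namely time in treatment and visit frequency.

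H2 in section 1.5 is about change in PHQ-9 and GAD-7 over time. In the research plan that follows the IRB form, the Data analysis paragraph names descriptive plots, Cohen's d and one test: "A *t*-test will be used to examine treatment differences in patient outcomes". It gives no time point, analysis set or method for missing scores.

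**The concern.** The plan promises 3-month scores for all patients but has no procedure that would produce one for a patient who has stopped attending. Scores arise from routine care, and attendance is plausibly related to symptoms. Some patients may leave because they are better, others because they are not improving. The mix could differ between groups.

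If so, the available scores are a selected sample, and the difference and Cohen's d computed from them describe that sample rather than the patients treated. The pilot is meant to prepare a larger trial, so a distorted effect size would be carried into its planning. Descriptive estimates are as exposed to this as tests are.

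**Working it through.** The documents state no effect size, SD, dropout rate or follow-up completeness, so there is no figure of theirs to reproduce. The calculation below shows only how much selective recording could matter.

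**Inputs, all assumed.** Mean PHQ-9 of 11 in usual care and 8.5 in modBA, the same at the last in-treatment visit and at 3 months; SD 5; correlation 0.7 between the two scores; scores clipped to 0–27; 2,000,000 simulated patients per group. The chance of having a 3-month score depends on the last in-treatment score, in bands below 5, 5 up to 10, and 10 or more.

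**Formula.** True difference = mean of all usual-care scores minus mean of all modBA scores = 11.03 − 8.59 = 2.44. Observed difference = the same subtraction among patients who have a score. A positive value favours modBA.

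| Chance of a score by band | Score available, usual care / modBA | Observed means | Observed difference | Share of true |
|---|---|---|---|---|
| 50/70/85% in both groups | 76% / 71% | 11.47 − 9.16 | 2.31 | 95% |
| 20/50/85% in both groups | 67% / 56% | 12.04 − 9.95 | 2.09 | 85% |
| 10/40/90% in both groups | 66% / 52% | 12.37 − 10.44 | 1.92 | 79% |
| 20/50/85% in modBA, flat 80% in usual care | 80% / 56% | 11.03 − 9.96 | 1.08 | 44% |
| 20/50/85% in usual care, flat 80% in modBA | 67% / 80% | 12.03 − 8.59 | 3.44 | 141% |

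With the nominal SD of 5, the true d is 2.44/5 = 0.49. The last two rows give 1.08/5 = 0.22 and 3.44/5 = 0.69.

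**Does using the recorded scores help?** In all five patterns, conditioning on the last in-treatment score brings the difference back to between 2.43 and 2.45. This works because, by construction, missingness here depends only on a recorded score.

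**When missingness depends on the unrecorded score.** A second simulation let the chance of a score depend on the 3-month value itself (assumed means 10 and 7.5, SD 5, true difference 2.4).
- Recorded for 30% of patients below 5 and 80% of the others, in both groups: 1.93.
- No patient below 5 recorded, others 80%, in both groups: 1.46.
- Recorded at random for 70%: 2.40, no bias.
- Recorded for 50% of patients at 10 or more and 80% of the others, in both groups: 2.24.
- modBA loses mainly patients below 5 (30% against 80%) and usual care mainly those at 10 or more (50% against 80%): 0.29.
- The reverse of that: 3.89.

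A model on recorded scores is not guaranteed to correct these cases, hence the sensitivity analysis in the fix.

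**The case against.** A reader might infer that the 3-month scores exist mainly for patients still in treatment, that remitted patients drop out, and that the comparison is therefore distorted against the better group. The documents do not support that.
- Nothing says when patients at this clinic stop care or that remitted patients leave.
- The limit of 10 weekly sessions in the research plan belongs to PST-PC, not to modBA or usual care here.
- Section 10.7 withdraws patients who become acutely suicidal and need hospitalization or more specialized treatment, which is a loss at the severe end.
- A different contact pattern under modBA is possible, but section 5.1 says patients' clinical visits will not change.

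These points stand, and they are why no direction is claimed.

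The t-test is not tied to the 3-month value either. The paragraph naming it follows a description of portal assessments before and after treatment, which itself needs reconciling with section 5.1. This also stands: the bias arises if the stated test is applied to the 3-month scores, and no other method is offered for them.

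Finally, the pilot is descriptive, it treats attrition as something to measure, and the bias can be small against the noise. In the 20/50/85% pattern common to both groups, about 27 and 22 of 40 patients have scores. The standard error is then 5 × √(1/27 + 1/22) = 1.44, against a bias of 2.44 − 2.09 = 0.35, about a quarter of it. If only modBA loses improved patients (about 32 and 22 with scores), the standard error is 5 × √(1/32 + 1/22) = 1.38 and the bias is 2.44 − 1.08 = 1.36, about as large. The objection limits the severity but does not remove the point.

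**Conclusion.** The concern holds in a limited form. It is a document fact that the 3-month scores are promised for all patients, come only from routine records, have no start point or window, and have no missing-data method. That their absence depends on outcome, or differs by group, is plausible but not stated anywhere.

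Under the assumed inputs of the first simulation, a true difference of 2.4 is seen as 1.9 to 2.3 when both groups lose improved patients by the same rule, and as 1.1 or 3.4 when only one group does. Scores missing at random would give no bias. The sizes rest entirely on assumed means, SD, correlation and availability. What does not rest on them is that the plan could not tell these cases apart. The change is worth making because it uses data already being extracted, but it does not invalidate the pilot.

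**What to change.** 1. Base the H2 comparison of change over time on all recorded weekly PHQ-9 and GAD-7 scores of all patients, from an index visit defined the same way in both groups to a fixed common horizon (for example 12 weeks). Fit a repeated-measures mixed model, so that patients who leave care still contribute the scores already recorded.
2. State that this is valid only if missingness depends on recorded scores. Add a simple sensitivity analysis for scores not missing at random: for example, shift the unrecorded scores up or down by a fixed amount, separately by group, and report where the conclusion changes.
3. Define the start point and window of the 3-month value and keep it as a descriptive secondary outcome.
4. Report by group the number with a 3-month score, the last in-treatment score of those with and without one, and the treatment-duration and visit-frequency data.
5. Reconcile section 5.1 with the research plan's description of when and how patient outcomes are collected.

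The cost is a little more analysis work and the need to settle an index visit for usual-care patients who are already in treatment. No new data collection is required. The price in interpretation is that the 3-month result supports no claim of sustained benefit.
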